The safety of USVCAP formulation in Type 2 Diabetes Mellitus Subjects Uncontrolled with Metformin Hydrochloride Treatment was determined by incidence and severity of treatment emergent adverse events (TEAEs) that occurred during the study period, including occurrence of hypoglycaemic episodes in each treatment group during the study period; and change in laboratory investigations post 12-week administration of USVCAP. Efficacy of the treatment was assessed by change in glycated haemoglobin (HbA1c) level post 12-week twice daily administration of selected fixed dose of USVCAP (75 IU, or 150 IU or 300 IU) from baseline, comparison of change in HbA1c between the 3 fixed dose levels studied to examine dose response relationship post 12-week administration of USVCAP and change in FPG and 2-hour PPG levels in each treatment group post 12-week administration of USVCAP. The immunogenicity was assessed by evaluating incidence of treatment-emergent antibody response (TEAR).

Selection of Study Population

Inclusion Criteria

- 1. Male or female aged 35 to 60 years (both inclusive)
- 2. Type 2 diabetes mellitus diagnosed < 2 years prior to enrolment
- 3. Glycated haemoglobin level $\ge 7\%$ and $\le 9.5\%$
- 4. On stable oral monotherapy with metformin hydrochloride (1000 mg to 2500 mg/day) and regular diet and exercise regimen at least 12 weeks prior to enrolment
- 5. Body mass index between 18 to 30 kg/m2
- 6. Ability to perform capillary blood glucose measurements

- 7. Willing to provide informed and written consent for the clinical trial
- 8. Able to comply with all requirements of clinical trial protocol

Exclusion Criteria

- 1. Subject with history or evidence of hypersensitivity to insulin or metformin hydrochloride or its excipients
- 2. Suffering from type 1 diabetes mellitus
- 3. Received treatment with sulphonylureas or alphaglucosidase inhibitors, Glucagon-like peptide-1 (GLP-1) receptor agonists or Sodium-glucose co-transporter 2 (SGLT2) inhibitors or meglitinides or pramlintide or thiazolidinediones within 3 months prior to enrolment
- 4. Previously treated with insulin within 3 months prior to enrolment
- 5. History of episodes of hypoglycaemia during 3 months prior to enrolment.
- 6. Reduced awareness of hypoglycaemia or inability to identify and tackle hypoglycaemic episodes
- 7. History of substantial weight loss defined as 5% decrease in body weight within the last 6 months
- 8. Medical history of unstable angina within 1 year prior to enrolment

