There was a run-in period/s of 1 week with each lower dose/s prior to initiation of the assigned fixed dose of USVCAP (Table 2). Upon completion of the run-in period/s, the subjects received the assigned fixed dose of USVCAP further for 12 weeks.

The Investigator considered the dose increase for each subject in Group B and Group C only if there was no evidence of lack of tolerability with dose/s of IP prescribed during run-in period/s and that the safety of the subject was unlikely to be compromised after administration of subsequent higher dose/s of the IP.

The dose increase at each DE visit was considered only after laboratory test results for FPG and 2-hour PPG levels were available to the Investigator.

For subjects in Group B (USVCAP 150 IU BD for 12 weeks):

- Run-in period
 - USVCAP 75 IU BD: Day 1 until Day 7
- Treatment period
 - USVCAP 150 IU BD: Day 8 until Day 91

For subjects in Group C (USVCAP 300 IU BD for 12 weeks):

- Run-in periods
 - USVCAP 75 IU BD: Day 1 until Day 7: 75 IU BD
 - USVCAP 150 IU BD: Day 8 until Day 14
- Treatment period
 - USVCAP 300 IU, BD: Day 15 until Day 98

The USVCAP doses were administered as per the trial protocol until the EOT. The subjects were withdrawn from the trial if there was requirement for change in dose during the treatment period (including run-in period and/or assigned fixed dose period), due to any reason(s).

Mode of administration: 1 hour before breakfast and dinner, orally with water

Duration of Treatment:

Treatment period: Each subject was treated with assigned fixed dose of USVCAP (Group A or Group B or Group C) for 12 weeks.

Overall duration of treatment with IP (including run-in period/s):

- Group A=12 weeks
- Group B=13 weeks
- Group C=14 weeks

During the post-treatment follow-up period, subjects were advised treatment for T2DM as per standard treatment guidelines.

Non-investigational Product

It was metformin hydrochloride capsules 250 mg, 500 mg, 850 mg or 1000 mg doses.

Dosage: Subjects continued their pre-study oral anti-diabetic monotherapy (i.e. metformin hydrochloride) as per pre-study dose and regimen from screening until the EOT, the dose adjustment for which, was not allowed during the entire treatment period.

Mode of administration: Orally with water along with meals

Duration of Treatment

• Approximately 17-19 weeks based on the randomized treatment group (i.e. Group A, Group B, or Group C).

Treatment during Post-Treatment Follow-Up Period:

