The efficacy assessments HbA1c, FPG and 2-hour PPG were assessed at the central laboratory identified for the study.

It was performed as follows:

- At screening to confirm the eligibility of the subject in the study
- During the treatment period and at EOT to evaluate to assess the safety and the treatment response
- At the EOS to evaluate the post-treatment safety of the subjects after twice daily administration of IP for 12 weeks

The blood samples for HbA1c, FPG and 2-hour PPG were withdrawn from the subject for the following tests:

- Glycated haemoglobin at Visit 1 and Visit 7
- Fasting plasma glucose level under fasting condition i.e. at least 8–10 hours of overnight fasting at Visits 1, 3, 4, 6, and 7 for all subjects

For Group B subjects: Prior to Visit DE 1

For Group C subjects: Prior to Visit DE 1 and Visit DE 2

• Postprandial glucose level (2-hours after meal) at Visits 1, 3, 4, 6 and 7 for all subjects. For Group B subjects: Prior to Visit DE 1

For Group C subjects: Prior to Visit DE 1 and Visit DE 2

• All samples were sent to central laboratory for evaluation. FPG and 2-hour PPG test results at Visit DE 1 and Visit DE 2 should be available prior to dosing.

Capillary glucose measurements

Capillary glucose measurements were performed by the subjects using a self-monitoring blood glucose device throughout the treatment period (from Visit 2 to Visit 7), once every week (mid-week).

During run-in period(s) (from Visit 2 to DE 1 [in Group B subjects] and from Visit 2 to Visit DE 1 and from Visit DE 1 to Visit DE 2 [in Group C] subjects), capillary glucose measurements were performed at mid-week.

The capillary glucose measurements were performed at the following 4 time points:

- Fasting: After 8 hours of overnight fast
- 2-hours post-breakfast
- 2-hours post-lunch
- 2-hours post-dinner

The measurements for all 4 timepoints were performed on the same day. All capillary glucose measurements were recorded by subject in the respective visit subject diary.

Hypoglycemia

It was important for subjects in the study to recognize signs and symptoms of hypoglycemia. Subjects enrolled in the study were educated on signs and symptoms of hypoglycemia and were instructed to keep glucose tablets handy & take 4 glucose tablets (total 15 -20 grams of glucose) immediately to treat hypoglycemia, if it occurs.

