- Renal function tests: Serum creatinine, BUN, sodium, potassium, chloride, and eGFR. Serology tests: human immunodeficiency virus, hepatitis B virus, and hepatitis C virus tests (only at Visit 1)
- At Visit 1, 7 and 8
 - Urine samples were collected for: Urine pregnancy test (UPT): Only for females of childbearing potential or who are ≤ 1 year postmenopausal prior to enrolment
- At Visits, 1, 3, 4, and 6:
 - Fasting plasma glucose level (also prior to dosing at Visit DE 1 and DE 2);
 - 2-hour PPG level (also prior to dosing at Visit DE 1 and DE 2)
- At Visit 1 only:
 - Haematology: RBCs count, Hb, platelet count, WBCs count including differential count (only at Visit 1)
 - Serology tests: human immunodeficiency virus (HIV), hepatitis B virus (HBV), and hepatitis C virus (HCV) tests
 - Urinalysis: routine examination (also at Visit 8)
 - Urine samples were collected for the following tests
 - At Visit 1, 7, and 8: Urine pregnancy test (UPT): Only for females of childbearing potential or who are ≤ 1 year postmenopausal prior to enrolment
 - At Visit 1 only: Urinalysis: routine examination

Any additional laboratory tests if required during the study period could be done at local accredited laboratory.

Immunogenicity Assessment: Insulin Antibody test - Anti-insulin antibody (AIA)

The immunogenicity of the IP was assessed using validated assays. Blood samples (1 x 3.5 mL) were collected at screening visit (Visit 1), End of treatment visit (Visit 7) and Post treatment follow-up visit (Visit 8) for testing presence of anti-insulin antibodies to the IP. The procedure for sample handling, storage and analysis was provided in the central laboratory manual.

Emergency Contact

In case of any emergency, the site contacted the medical monitor from the CRO. The medical monitor provided guidance in case of any emergency related to safety of the subject.

Other Study Assessment

Body Weight, Waist circumference and Body mass index

Body weight was measured at every study visit in kg. Body mass index (BMI) (kg/m^2) and waist circumference (cm) was calculated at all study visits, except Visit DE 1 and Visit DE 2.

Body mass index (BMI) was calculated by formula:

$$BMI = \frac{Weight \ (kg)}{height^2 \ (m)^2}$$

Appropriateness of Measurements

All clinical measurements were performed using standard methods that were generally recognized as being reliable, accurate, and relevant.

Primary Variable(s):

Efficacy Assessment:

- Glycated haemoglobin (HbA1c)

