Summary tables were provided for prior/concomitant medications in the study.

Immunogenicity analyses

Partial correlation was used to measure the relationship between the percent change in HbA1c and percent change in anti-insulin antibodies with absolute change in total insulin dose as covariate from baseline to Visit 7 and Visit 8. Change in level of serum anti-insulin antibodies from baseline to Visit 7 and Visit 8 were compared through paired t-test within each treatment arms.

Statistical Significance

The level of significance in the primary analysis were set to 5%. The analyses was performed upon completion of the main trial period. All secondary analyses were also be performed at the 5% significance level.

Replacement of Subjects

The subject who discontinued from trial/withdrawn from the study treatment were not replaced.

Withdrawn Subject Data Collection

The subject could withdraw their consent from the trial, or this could be the Investigator's decision to discontinue the subject from trial; if they decided to do so, at any time and irrespective of the reason all efforts should be made to document the reason for treatment withdrawal/discontinuation from the trial (see section 11.5.1) and this should be documented in the e-CRF.

The Investigator/designee involved in the study documented the reason for the subject withdrawal as follows:

Subject's voluntary withdrawal of consent

Subject's non-compliance to the IP: Repeated missing of study medication doses

Protocol violation: Repeated non-follow-up for safety or efficacy procedures required for the study. Protocol violation may be also considered when the subject is not included as per protocol-defined eligibility criteria.

Any AE or SAE requiring subject withdrawal in the opinion of the Investigator: An AE form must be completed. Clinically significant abnormal value not explained by a laboratory error or being not a known or abnormal value commonly observed in this type of population was also considered as an AE or SAE, and recorded on AE form as applicable.

Requirement of prohibited medication: Recording of the details of prohibited medication were completed on the concomitant medication CRF page and the subject were withdrawn from the study.

Requirement of dose reduction for both IP and non-IP: If there was requirement for change in dose of the IP (which is not mentioned in the protocol) or non-IP at any point of time during the study period, the subject were withdrawn from the study.

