
Study termination by Sponsor: Upon notification of the sponsor for termination of the study

Study termination based on the advice by CDSCO or any other competent authority: If the regulatory authority(ies) directly connects to the site/CRO to terminate the study, the same was immediately done by the Investigator/information were communicated to the sites. The CRO must notify the site regarding such communications. In case of communications directly reaching the Investigator, the Investigator must inform the CRO designee (e.g. study site monitor) or both Sponsor designee and CRO designee

Any, other reason: If none of the above-mentioned reasons are applicable, then the reason for subject withdrawal were mentioned; "any other reason" and the reason were specified on the eCRF page. In case of pregnancy, the subject's study treatment must permanently stop and study discontinuation and early withdrawal procedures should be conducted.

Determination of Sample Size

It was estimated that 52 evaluable subjects per dose group were needed to be enrolled in each treatment group assuming a reduction of 0.5 in HbA1c, common standard deviation (SD) of 1.0 at baseline and at Week 12 in each dose group with 90% power and 2.5% level of significance. However, 13 extra subjects, accounting for 65 subjects per group in total were enrolled into this study with an aim to compensate for an estimated drop-out rate of 20%. Thus, a total number of 195 subjects were to be randomly assigned to either of the three dose (treatment) groups in this study in the ratio of 1:1:1. The detailed description of sample size calculation is represented in the table below:

Single Mean - Paired t-test				
Pre-test mean	7.5			
Post-test mean	7			
Mean Difference from Pre-to Post test	0.5			
Standard deviation in Pre-test	1			
Standard deviation in Post-test	1			
Effect size	0.5			
Power (%)	90			
Alpha Error	2.5			
1 or 2 sided	2			
Minimum required sample size for each selected fixed dose treatment	52			

group	
Minimum required sample size for all three-selected fixed dose treatment	156
groups	
Considering 20% drop-out, required sample size for each selected fixed	65
dose treatment group per	
Considering 20% drop-out, required sample size for all three-selected	
fixed dose treatment groups	195

Missing Data

The missing observations were imputed using Last Observation Carried Forward (LOCF) appropriately.

Procedures for Reporting Deviations from Original Statistical Plan

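### The HbA1c–antibody correlation is planned to Visit 8, where no HbA1c is scheduled, and its dose covariate at Visit 7 is only a stand-in for treatment arm

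*Combined protocol and SAP*

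**What the plan says.** Under Immunogenicity analyses: "Partial correlation was used to measure the relationship between the percent change in HbA1c and percent change in anti-insulin antibodies". The sentence then names its covariate and its two time points: "with absolute change in total insulin dose as covariate from baseline to Visit 7 and Visit 8". The next sentence plans paired t-tests of antibody level within each arm at the same two visits. Only that sentence mentions arms; whether the correlation is pooled or by arm is not stated.

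On HbA1c sampling, Efficacy Assessment lists "Glycated haemoglobin at Visit 1 and Visit 7". Table 2 and Laboratory Investigations agree, and the procedure list for Visit 8 contains no HbA1c. Earlier in Efficacy Assessment, however, a general sentence covering HbA1c, FPG and 2-hour PPG says they were also performed "At the EOS to evaluate the post-treatment safety of the subjects after twice daily administration of IP for 12 weeks". Antibody samples are scheduled at Visits 1, 7 and 8 (Immunogenicity Assessment).

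On dose, each arm has a fixed twice-daily dose, and under Investigational Product "The subjects were withdrawn from the trial if there was requirement for change in dose during the treatment period". Exclusion criterion 4 removes subjects "Previously treated with insulin within 3 months prior to enrolment". Other anti-diabetic drugs are prohibited on study; treatment after the last dose is left to standard guidelines.

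On missing data: "The missing observations were imputed using Last Observation Carried Forward (LOCF) appropriately". No antibody scale, detection limit, or rule for zero or undetectable baselines is given.

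**The concern.** A correlation needs both variables measured at the same visit, and a partial correlation needs a covariate that carries information beyond the grouping. The Visit 8 analysis lacks the first. The Visit 7 analysis has a covariate whose name suggests individual dose titration, in a trial that does not titrate individually.

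Immunogenicity is the trial's only stated secondary objective, and this is the only planned analysis that relates antibodies to glycaemic response. A Visit 8 coefficient reported from carried-forward HbA1c could be read as evidence about the post-treatment period, although it would contain no post-treatment HbA1c. A Visit 7 coefficient described as dose-adjusted could be read as controlling for individual exposure.

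**Working it through.** The plan gives no numerical figure for this analysis, so there is none to reproduce. The check compares the schedule with the formulae.

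**Step 1: what is measured when** (Table 2, the visit descriptions, Laboratory Investigations, Immunogenicity Assessment).

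| | Visit 1 | Visit 7 | Visit 8 |
|---|---|---|---|
| HbA1c | yes | yes | not scheduled |
| Anti-insulin antibodies | yes | yes | yes |
| USVCAP | not started | 12 weeks at assigned dose completed | stopped |

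Write H and A for HbA1c and antibody level. The Visit 8 correlation needs 100 × (H8 − H1)/H1, and H8 is not scheduled. If carry-forward is applied, H8 is set to H7, and the quantity becomes 100 × (H7 − H1)/H1, the Visit 7 change again. It would be paired with 100 × (A8 − A1)/A1. The scheduled gap is 114 − 85 = 121 − 92 = 128 − 99 = 29 days in Groups A, B and C. Every HbA1c value used at Visit 8 would be imputed.

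**Step 2: the covariate at Visit 7.** Baseline insulin dose is 0 for eligible subjects. Change in daily dose is therefore 2 × 75 = 150, 2 × 150 = 300 and 2 × 300 = 600 IU/day.

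The partial correlation of x and y given c is

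r = (rxy − rxc·ryc) / √[(1 − rxc²)(1 − ryc²)].

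- Within one arm, c is constant, its variance is 0, and rxc and ryc are 0/0, so the formula is undefined. Under the residual definition a constant removes nothing, and the result is the ordinary correlation rxy. Either way there is no adjustment.
- Pooled, c takes three values and the analysis runs. In a simulation with invented data (51 per arm, n = 153), rxy = 0.183, rxc = −0.141 and ryc = 0.038, so r = (0.183 + 0.005)/√(0.980 × 0.999) = 0.19. But c is then arm coded 1:2:4. It forces the shift from B to C (300 IU/day) to be twice that from A to B (150 IU/day).
- If total dose means cumulative dose, the scheduled totals are still set by arm: A 84 × 150 = 12,600 IU; B 7 × 150 + 84 × 300 = 26,250 IU; C 7 × 150 + 7 × 300 + 84 × 600 = 53,550 IU. Compliance and early exit would add some within-arm variation.

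**Step 3: the covariate at Visit 8.** USVCAP has stopped, so its change from baseline is 0 − 0 = 0 for everyone. Total insulin dose is also constant if nobody starts insulin in follow-up. That is an assumption, because follow-up treatment is not specified.

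**Step 4: percent change in antibodies.** 100 × (A7 − A1)/A1 is undefined at A1 = 0. For illustration, a follow-up level of 2 units is +100% from a baseline of 1, +400% from 0.4 and +1,900% from 0.1. If 25%, 50%, 75% or 90% of 153 subjects had a zero baseline and dropped out of the calculation, about 115, 76, 38 or 15 would remain. These shares are assumptions; the documents give none.

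**The case against.** The strongest reply is that the Visit 7 analysis can be run. A reader might infer that the correlation cannot be computed at all because the covariate is a constant. The documents do not support that: nothing says the analysis is by arm, and pooled the covariate has three values. Nor is the within-arm variance shown to be exactly zero. Subjects who withdraw early have the Visit 7 assessments at withdrawal, possibly on a run-in dose in Groups B and C, and total dose is not defined. Nor is the covariate shown to be zero for all at Visit 8, since insulin may have been started in follow-up. All of this stands. It leaves a covariate that mainly codes arm; and insulin started after Visit 7 would post-date the carried-forward HbA1c, so it would not be a sound adjustment for it.

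A reader might also infer that percent change is bound to fail because subjects had no recent insulin. That does not follow: the exclusion covers three months and says nothing about measured antibody levels. Only the missing rule is established.

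The end-of-study sentence in Efficacy Assessment could be taken to supply a Visit 8 HbA1c. It conflicts with the visit-specific list that follows it in the same section, with Table 2 and with the Visit 8 procedures, so it calls for reconciliation and does not settle the matter. The carry-forward rule is qualified by appropriateness, and applying it to a never-scheduled test is an inference. Without it, though, the Visit 8 analysis simply has no HbA1c data.

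Finally, the text refers to a separate, more detailed SAP that is not included. It may define pooling, dose and coding, but it cannot create HbA1c samples that were not scheduled. Nor is this the only immunogenicity measure: incidence of treatment-emergent antibody response is named in the discussion of study design, and level is tested within arms.

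**Conclusion.** The Visit 8 correlation is wrong as written: under the schedule it has no observed HbA1c, and carry-forward would only pair Visit 7 HbA1c with off-treatment antibodies. This rests on the detailed lists prevailing over the single end-of-study sentence.

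The Visit 7 correlation is computable if pooled, but its covariate is misnamed. It is essentially arm (150, 300 or 600 IU/day), empty within an arm and a straight-line code across arms, and the plan does not say which use is meant. This assumes insulin-free baselines and adherence to the fixed-dose rule.

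The percent-change weakness is conditional on baseline antibody values that the documents do not give. The effect is confined to a secondary immunogenicity analysis; the primary HbA1c comparison is untouched.

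**What to change.** - Delete the Visit 8 correlation. Report Visit 8 antibodies by the within-arm change already planned and descriptively.
- Reconcile the end-of-study sentence in Efficacy Assessment with Table 2 and the visit lists. If HbA1c was in fact collected at Visit 8, say so and correct the lists.
- At Visit 7, state that the analysis is pooled and replace the dose covariate with treatment group as a factor. This uses two parameters instead of one and drops the linear assumption.
- Optionally, replace percent change in antibodies by a log ratio with a fixed rule for values below the assay limit, or by antibody status.
- Change in Planned Analysis currently reports nothing. Because the text describes a completed study, disclose the change in the clinical study report, and label any replacement analysis as not pre-planned.

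The cost is wording, a re-run of one Visit 7 analysis if it has been done, and the loss of one coefficient with no scheduled HbA1c behind it. No new data are needed.

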The proposed oral formulation USVCAP addresses most concerns regarding delivery of insulin through oral route. USVCAP is a formulation containing recombinant human insulin and excipients. The excipients are added to promote absorption of active drug substance in jejunum. The technology used in the unique formulation, can enhance the passage of large molecules such as peptides, and proteins across the intestinal wall from lumen into the bloodstream. The formulation is stable and is designed in such a way that the dry powder dissolves rapidly in the liquid in the small intestine, bringing all components of the formulation (including peptides) in contact with the cell wall at the same time.¹¹

The rationale for combining insulin and oral drug therapy is derived from a better understanding of the pathophysiology of non-insulin dependent diabetes mellitus and of the mechanisms of action of the oral drugs:

- 1) T2DM subjects are both insulin-deficient and insulin-resistant, thus requiring quite high doses of exogenous insulin
- 2) Peripheral insulin delivery leads to hyperinsulinemia which could play a role in the pathogenesis of late diabetic complications;
- 3) Metformin hydrochloride (by improving glucose metabolism and insulin sensitivity) and alpha-glucosidase inhibitors (by slowing down the digestion of complex carbohydrates and sucrose) are able to reduce the amounts of insulin needed to control postprandial hyperglycaemia¹⁵

For subjects who fail to respond to the initial therapy, there are several agents that are available and can be used with metformin. Insulin is the preferred second-line medication for subjects with increased HbA1c or with symptoms of hyperglycaemia despite initial therapy with metformin and lifestyle intervention.⁶ Most recommendations agree that if HbA1c level is > 8.5-9% irrespective of the dose of oral anti-diabetic drug (OAD), insulin should be initiated particularly in combination with metformin.¹⁶ The consensus statement by the American Association of Clinical Endocrinologists/ American College of Endocrinology (AACE/ACE) on the comprehensive T2DM management recommends insulin doses based on HbA1c levels (HbA1c < 8%; TDD: 0.1-0.2U/kg; HbA1c >8%; TDD: 0.2-0.3U/kg).¹⁷

The current study was undertaken to generate evidence on the safety, efficacy and immunogenicity of USVCAP Formulation in Type 2 Diabetes Mellitus Subjects Uncontrolled with Metformin Hydrochloride Treatment in real world settings.

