• During the post-treatment follow-up period, subjects were advised treatment for T2DM as per standard treatment guidelines

Investigational Medicinal Product Handling and Accountability

Dispensing, Packaging and Labelling

The IP was supplied by the sponsor designee/pharmacist to the sites sufficiently, as required for all the subjects. The Investigator/designee dispensed the treatment to subjects as per the randomization codes assigned by IWRS.

The dose and total number of capsule/s to be dispensed to the subject were as per the requirement of dosing at corresponding visit per each treatment group. The IP was supplied to the sites.

The label of IP included with the following information, but not limited to:

- Study Identification Code
- Kit Code
- Batch Number
- Manufacturing Date

- Expiry Date •
- Dose strength of each capsule
- Quantity statement •
- Direction for Use •
- Storage Condition •
- The statement "For Clinical Trial Use Only" •
- Sponsor/Manufactured by ٠

The label of the box containing IP included with the following information but not limited to:

- Study Identification Code •
- Kit Code •
- Batch Number •
- Manufacturing Date •
- Expiry Date •
- Quantity statement
- Direction for Use
- Storage Condition •
- Site Number •
- The statement "For Clinical Trial Use Only" •
- Sponsor/Manufactured by •

Handling, Storage, and Disposal

Investigational product

The IP was not used beyond the expiration date stamped on the label/box. Do not freeze or expose to excessive heat or direct sunlight. The IP was stored between 2° to 8°C (both inclusive).

Study Drug Accountability Procedures

The Investigator was responsible for the overall conduct of the study. Under no circumstances, the Investigator allowed the IP to be used other than as directed by study protocol. An accurate record of the receipt of IP from Sponsor/designee, dispensing of the IP to subject and return/lost or destroyed IP by the subject was maintained. Upon completion of the study, the used and/or unused IP capsules and other supplies (if any) were shipped to Sponsor for storage or destruction as per sponsor's communication.

Identity of Investigational Products

The investigational product (IP) is USVCAP Formulation a solid oral dosage form in capsules. Each capsule contains IP in dose strengths 75 IU or 150 IU.

Method of Assigning Patients to Treatment Groups

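### The Visit 8 antibody test makes no allowance for non-study insulin started after end of treatment, so a rise first seen at Visit 8 may not be due to USVCAP alone

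*Combined protocol and SAP*

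**What the plan says.** Immunogenicity is the only secondary objective. Antibody samples are taken at screening, Visit 7 and Visit 8, "for testing presence of anti-insulin antibodies to the IP" (Immunogenicity Assessment). The planned test is given under Immunogenicity analyses: "Change in level of serum anti-insulin antibodies from baseline to Visit 7 and Visit 8 were compared through paired t-test within each treatment arms". A partial correlation of HbA1c change with antibody change is also planned, "with absolute change in total insulin dose as covariate from baseline to Visit 7 and Visit 8". The paired t-test has no such covariate. The study-design discussion also names the incidence of treatment-emergent antibody response (TEAR) as a measure, without saying at which visit it is counted.

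On treatment after Visit 7, the Study Treatment section says: "During the post-treatment follow-up period, subjects were advised treatment for T2DM as per standard treatment guidelines". Metformin is held fixed only until end of treatment.

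The study-design discussion gives the background on insulin. It states: "Insulin is the preferred second-line medication for subjects with increased HbA1c or with symptoms of hyperglycaemia despite initial therapy with metformin". It also reports that most recommendations agree that "if HbA1c level is > 8.5-9% irrespective of the dose of oral anti-diabetic drug (OAD), insulin should be initiated". On the product it says: "USVCAP is a formulation containing recombinant human insulin and excipients".

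The exclusion criteria bar insulin in the 3 months before enrolment. Concomitant medications are recorded at Visit 8 (Table 2), but the analysis section plans only summary tables of them. Missing observations are imputed by last observation carried forward (LOCF) where appropriate.

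**The concern.** The Visit 8 sample is meant to show the antibody response to USVCAP four weeks after the last dose. If some subjects start another insulin in that interval, their Visit 8 value can contain a response to it. Nothing shown says that the assay can tell the two apart. The exclusion criteria protect the baseline value against other insulin; no matching rule protects Visit 8.

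No arm is without USVCAP, so a within-arm test has nothing to offset such a contribution. Insulin starters would also tend to be the subjects with the highest Visit 7 HbA1c, so their number could differ by dose. What is at stake is how a rise first seen at Visit 8 is read. The Visit 7 antibody test and the HbA1c analyses are not touched.

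**Working it through.** **The plan's own figure.** There is none for the antibody analysis. The only calculated figure is the HbA1c sample size of 52 per arm. With effect size 0.5, two-sided alpha 2.5% and 90% power, the normal approximation gives ((2.241 + 1.282)/0.5)² = 49.6, so 50. The exact t calculation gives 53, with power 0.899 at 52. The figure reproduces closely, and nothing below depends on it.

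**Interval at risk (Table 2).** Visit 7 to Visit 8: 114 − 85 = 121 − 92 = 128 − 99 = 29 days.

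**How many might start insulin.** Inputs:
- 153/3 = 51 subjects per arm, all assumed to reach Visit 8.
- From the sample-size table: SD 1 and mean HbA1c falling from 7.5 to 7.0.
- Assumed: everyone above 8.5% (or 9%) at Visit 7 starts insulin, and nobody else does. HbA1c is taken as normal.

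Expected starters = 51 × [1 − Φ((cut − mean)/1)]:

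| Visit 7 mean | Cut 8.5% | Cut 9% |
|---|---|---|
| 7.0 (planned fall) | 51 × 0.067 = 3.4 | 51 × 0.023 = 1.2 |
| 7.5 (no change) | 51 × 0.159 = 8.1 | 51 × 0.067 = 3.4 |

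A check restricts baseline to the 7% to 9.5% entry range, with an assumed correlation of 0.5 between baseline and Visit 7. The shares are then 8.3% and 2.7% with the planned fall (4.2 and 1.4 subjects), and 19.9% and 8.3% with none (10.1 and 4.2 subjects). The order of magnitude is the same.

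**Effect on the paired t-test.** Simulation: n = 51, two-sided 5%, 40,000 runs, no USVCAP effect on antibodies. For k starters the antibody change is shifted up by d SD. The value of d is assumed, because the documents give no figure for it. Percentage of trials with a significant rise:

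| Starters k | d = 0.5 | d = 1 | d = 2 |
|---|---|---|---|
| 0 | 2.5 | 2.5 | 2.5 |
| 1 | 3.0 | 3.3 | 3.8 |
| 3 | 4.0 | 5.4 | 9.1 |
| 8 | 7.3 | 16.2 | 40.4 |

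**Effect on TEAR, if it is counted at Visit 8.** Each new response among starters adds 1/51 = 2.0 percentage points to an arm's incidence. Three would add 3/51 = 5.9 points.

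**The case against.** **Was other insulin barred?** The prohibited-medication list covers any anti-diabetic drug other than metformin during the study, and needing a prohibited drug leads to withdrawal. The stated metformin duration of 17 to 19 weeks also sits awkwardly with stopping at end of treatment: 3 weeks of screening plus 12 to 14 weeks of dosing is 15 to 17. The text is therefore not fully consistent. But the sentence on guideline care is written specifically for follow-up and is the better guide to that period. If the general ban did apply, a starter would be withdrawn, and LOCF might then put the Visit 7 antibody value in place of Visit 8. The text does not say whether LOCF was meant for antibodies.

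**The insulin passage is background.** It gives the rationale for combining insulin with oral drugs and is not a rule for follow-up. It is conditional on raised HbA1c or symptoms, and it says that several other agents can be added to metformin. This stands: it shows that insulin is possible, not that it was usual. No passage shows that anyone started it.

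**Likely starters may already have left.** Subjects with high fasting glucose are withdrawn during treatment, and 20% drop-out is planned for. Both would lower the counts above.

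**Stronger readings that the documents do not support.** A reader might infer that no antibody rise in this trial can be credited to USVCAP. That does not follow: Visit 7 falls the day after 12 weeks of assigned dosing, before guideline follow-up care begins, and has its own test. A reader might also infer that a weaker dose will be shown to be more immunogenic. The plan tests antibody levels only within arms, so that would be an informal comparison. The 16% figure needs 8 starters, which means no HbA1c effect and insulin for everyone above 8.5%.

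**The separate SAP is not shown.** The protocol refers to a more detailed plan. A rule there would settle the matter.

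**Conclusion.** The point holds for Visit 8 only. As the text stands, the planned test would count a response to another insulin as part of the change after USVCAP, so a rise that is new at Visit 8 could partly reflect that insulin.

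The size is unknown and probably small. With the planned HbA1c fall and the 8.5% or 9% threshold there would be about 1 to 3 starters per arm. At an assumed 1 SD shift, that takes the chance of a false significant rise from 2.5% to about 3% to 5%. With one starter it is negligible. These figures rest on the assumed uptake rule, the assumed shift, and all 51 subjects per arm reaching Visit 8. This is a worthwhile minor improvement and does not call the trial's main conclusions into question.

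**What to change.** 1. Make Visit 7 the main immunogenicity time point.
2. From the concomitant-medication records at Visit 8, list by arm the subjects who started non-study insulin after Visit 7. If there are none, the matter is closed.
3. Report the Visit 8 paired t-test, and TEAR if it is counted at Visit 8, both for all subjects and without values taken after non-study insulin.
4. Do not fill in Visit 8 antibody values by carrying Visit 7 forward.

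The cost is one flag from data already recorded and one extra analysis run, with no new visit or sample. If the analysis is added after the fact, it should be labelled so in the study report, as the plan already requires. The version without starters drops subjects with poorer Visit 7 HbA1c, who may differ in antibody response, so it is a sensitivity analysis to be read beside the all-subjects result and not a replacement for it. The prohibited-medication and withdrawal rules need no rewriting.
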